	Baseline	30 minutes	60 minutes	120 minutes	180 minutes	Max Increase	Max Decrease
Heart Rate, beats/min							
N	x	x	x	x	x	x	x
Mean (SD)	xxx.x (xxx.x)	xxx.x (xxx.x)					
Median	xxx	xxx	xxx	xxx	xxx	xxx	xxx
[Min-Max]	[xxx-xxx]	[xxx-xxx]	[xxx-xxx]	[xxx-xxx]	[xxx-xxx]	[xxx-xxx]	[xxx-xxx]
Systolic BP, mmHg							
N	x	x	x	x	x	x	x
Mean (SD)	xxx.x (xxx.x)	xxx.x (xxx.x)					
Median	xxx	xxx	xxx	xxx	xxx	xxx	xxx
[Min-Max]	[xxx-xxx]	[xxx-xxx]	[xxx-xxx]	[xxx-xxx]	[xxx-xxx]	[xxx-xxx]	[xxx-xxx]
Diastolic BP, mmHg							
N	x	x	x	x	x	x	x
Mean (SD)	xxx.x (xxx.x)	xxx.x (xxx.x)					
Median	xxx	xxx	xxx	xxx	xxx	xxx	xxx
[Min-Max]	[xxx-xxx]	[xxx-xxx]	[xxx-xxx]	[xxx-xxx]	[xxx-xxx]	[xxx-xxx]	[xxx-xxx]

SD= standard deviation; BP= blood pressure.

^a Positive value indicates an increase from baseline and negative value indicates a decrease.

Figure 4: Vital signs before and after administration of G-Pen™ by age group and by treatment dose for subjects aged 12.0-<18.0

BP= blood pressure.

Table 16: Incidence of any injection site discomfort by age group and by treatment dose for subjects aged 12.0-<18.0

Age Group	G-Pen™ Dose	Incidence of Any Injection Site Discomfort ^a					
		10 minutes		30 minutes		180 minutes	
		n	%	n	%	n	%
2.0-<6.0 years (N=X)	0.5 mg	x	x.x	x	x.x	x	x.x
6.0-<12.0 years (N=X)	0.5 mg	x	x.x	x	x.x	x	x.x
12.0-<18.0 years (N=X)	1.0 mg	x	x.x	x	x.x	x	x.x
12.0-<18.0 years (N=X)	0.5 mg	x	x.x	x	x.x	x	x.x

^a Any injection site discomfort is defined as Faces Pain Scale – Revised (FPS-R) score >0.

Table 17: Incidence of erythema after administration of G-Pen™ by age group and by treatment dose for subjects aged 12.0-<18.0

Age Group	G-Pen™ Dose	Incidence of Erythema ^a					
		10 minutes		30 minutes		180 minutes	
		n	%	n	%	n	%
2.0-<6.0 years (N=X)	0.5 mg	x	x.x	x	x.x	x	x.x
6.0-<12.0 years (N=X)	0.5 mg	x	x.x	x	x.x	x	x.x
12.0-<18.0 years (N=X)	1.0 mg	x	x.x	x	x.x	x	x.x
12.0-<18.0 years (N=X)	0.5 mg	x	x.x	x	x.x	x	x.x

^a Erythema formation is defined as Modified Draize Scale score for erythema >0.

Table 18: Incidence of edema after administration of G-Pen™ by age group and by treatment dose for subjects aged 12.0-<18.0

Age Group	G-Pen™ Dose	Incidence of Edema ^a					
		10 minutes		30 minutes		180 minutes	
		n	%	n	%	n	%
2.0-<6.0 years (N=X)	0.5 mg	x	x.x	x	x.x	x	x.x
6.0-<12.0 years (N=X)	0.5 mg	x	x.x	x	x.x	x	x.x
12.0-<18.0 years (N=X)	1.0 mg	x	x.x	x	x.x	x	x.x
12.0-<18.0 years (N=X)	0.5 mg	x	x.x	x	x.x	x	x.x

^a Edema formation is defined as Modified Draize Scale score for edema >0.

Figure 5: Local tolerability by age group and by treatment dose for subjects aged 12.0-<18.0

[figure not shown]

Table 19: Time of onset and duration of discomfort and discomfort description by age group and by treatment dose for subjects aged 12.0-<18.0				
	2.0-<6.0 years (N=X^{a,b})	6.0-<12.0 years (N=X^a)	12.0-<18.0 years with 1.0 mg (N=X^a)	12.0-<18.0 years with 0.5 mg (N=X^a)
Time of Onset, minute				
N	x	x	x	x
Mean (SD)	xx.x (xx.x)	xx.x (xx.x)	xx.x (xx.x)	xx.x (xx.x)
Median	xx	xx	xx	xx
[Min-Max]	[xx-xx]	[xx-xx]	[xx-xx]	[xx-xx]
Duration – n (%)				
< 1 minute	x (x.x)	x (x.x)	x (x.x)	x (x.x)
1-2 minutes	x (x.x)	x (x.x)	x (x.x)	x (x.x)
3-5 minutes	x (x.x)	x (x.x)	x (x.x)	x (x.x)
6-9 minutes	x (x.x)	x (x.x)	x (x.x)	x (x.x)
10-15 minutes	x (x.x)	x (x.x)	x (x.x)	x (x.x)
16-30 minutes	x (x.x)	x (x.x)	x (x.x)	x (x.x)
30-120 minutes	x (x.x)	x (x.x)	x (x.x)	x (x.x)
121-180 minutes	x (x.x)	x (x.x)	x (x.x)	x (x.x)
Discomfort Description ^c				
Pain (e.g. throbbing, soreness, muscle ache) – n (%)	x (x.x)	x (x.x)	x (x.x)	x (x.x)
Itching – n (%)	x (x.x)	x (x.x)	x (x.x)	x (x.x)
Tingling, twitching, or numbness – n (%)	x (x.x)	x (x.x)	x (x.x)	x (x.x)
Irritation (e.g. burning, stinging) – n (%)	x (x.x)	x (x.x)	x (x.x)	x (x.x)

^aOnly those who reported having at least one discomfort post-injection are included in the table.

^bX subjects are not applicable because they are too young for comprehension.

^cA subject may report more than one discomfort.

Listing 3: Pregnancies and outcomes

Subject ID	Age group	G-Pen™ dose	Number of Embryos, Fetuses, and/or Infants	Outcome	Congenital Anomaly?	Gestational Age (weeks and days)	Gender	Weight (lbs)	Length (in)	Head Circumference (cm)

Appendix II: PHARMACOKINETIC ANALYSIS CONDUCTED BY Integrated Medical Development, New Jersey USA

1 PK Analysis Population

There is only one population for PK analysis. It is defined as all subjects randomized.

2 PK Endpoints

The following PK endpoints will be analyzed:

- C_{Max} , maximum concentration of G-Pen Glucagon
- T_{Max} , the time when maximum concentration of G-Pen Glucagon reached
- $AUC_{0-120min}$, area under the curve of G-Pen Glucagon from 0 to 120 minutes

3 Analysis variables

3.1 Handling of the missing values

The PK samples are drawn blood at -5, 0, 10, 20, 30, 45, 60, 90, 120, and 180 minutes post dose, with ± 2 minutes per collection for the samples from -5 and 0 minutes, and ± 5 minutes for later samples. The following procedures will be applied to handle any missing values of the PK:

- If PK at time 0 minute (T_0) is missing, then PK at -5 minute will be substituted. If both -5 minute and 0 minute PK are missing, then the PK at later minutes will be used to impute the PK at 0 minute. In such case, linear imputation will be used.
- If PK at 120 minute is missing, then cubic imputation will be used to impute the PK at 120 minute. Exception: if PK at 120 minute is missing and the last available PK is the C_{max} , i.e., PK never comes down, and then no imputation will be done.
- All other missing PK values will not be imputed

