9. After 5 minutes, a confirmatory plasma glucose measurement will be performed.
  - a. If plasma glucose remains  $< 80$  mg/dL, collect a second baseline PK blood sample, and begin administration of the study drug (see Section 9.3.2).
  - b. If plasma glucose has risen to  $\geq 80$  mg/dL, return to step 7b and repeat the process.
10. Following study dosing, plasma glucose will be measured every  $5 \pm 2$  minutes until 90 minutes post-dosing.

11. Additional blood samples will be collected at 10, 20, 30, 45, 60, 90, 120, and 180 minutes post-dosing, with  $\pm 5$  minutes per collection, and processed and stored at  $-80 \pm 20$  C for determination of plasma glucagon levels.
12. After completing all collections and procedures at 180 minutes post-dosing, the subject will be given a meal as per the standard practice at each site, and their usual dose of insulin. The subject can then leave the clinic after plasma glucose is confirmed to be between 70 and 180 mg/dL.
13. Local tolerability will be assessed as follows:
  - a. Subjects will complete age-appropriate questionnaires regarding injection site discomfort ([Appendix 1](#)) at  $10 \pm 5$  and  $30 \pm 5$  minutes post-dosing, and again at  $180 \pm 5$  minutes post-dosing if the FPS score reported at 30 minutes is  $> 0$ .
  - b. An investigator will use the modified Draize scales ([Appendix 2](#)) to assess erythema and edema formation at the injection site at  $10 \pm 5$  and  $30 \pm 5$  minutes following administration. Any injection site with a score  $> 0$  for either erythema or edema at 30 minutes post-dosing will be re-evaluated for both at  $180 \pm 5$  minutes post-dosing.
14. Adverse events reported by the subject or observed by an investigator will be recorded in Advantage eClinical and managed as medically appropriate.

If a subject exhibits signs of distress at any time post-dosing or if plasma glucose drops below  $< 70$  mg/dL, glucose tablets may be given at the discretion of the investigator. Signs and symptoms should be monitored and if the subject's condition fails to improve within 15 minutes, additional glucose tablets or other intervention (e.g., IV dextrose) may be given at the discretion of the investigator. Every attempt should be made to complete all remaining safety and efficacy evaluations, to the extent this can be done while safeguarding the subject.

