### Volume of Blood Draws

The maximum blood volume to be collected will not exceed 5% of the subject's blood volume. The number of blood draws will be reduced for subjects who do not weigh enough to allow for the full schedule to be completed. Early collections (-5 to 30 minutes) will be preferred over later blood draws, and PD samples will be prioritized over PK samples.

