3.2.1 C_{Max}

C_{Max} is defined as the maximum concentration of G-Pen Glucagon after time 0 minute.

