3.2.2 T_{Max}

T_{Max} is defined as time (min) when maximum concentration of G-Pen Glucagon reached after T_0 . If there are multiple C_{Max} following the injection, T_{Max} will be the first time when C_{Max} is reached. Actual time instead of protocol time will be used.

3.2.3 $AUC_{0-120min}$

$AUC_{0-120min}$ is calculated using Trapezoidal rule from T_0 to T_{120} . Actual time instead of protocol time will be used.

4 Statistical Analysis

The three PK variables defined in section 3.2 will be analyzed descriptive for the age groups and doses (2.0-<6.0yr 0.5mg, 6.0-<12.0yr 0.5mg, 12.0-<18.0yr 1mg, and 12.0-<18.0yr 0.5mg). Mean, standard deviation, median, minimum and maximum will be presented.

Individual figures of each subject each dose will be presented. Mean G-Pen Glucagon vs protocol time point will be presented for each age group and doses. Protocol time point will be used to allow aggregation.

5 Planned Output Table of Content

Tables	14.2.1.1	Glucagon : Cmax by age and dose
	14.2.1.2	Glucagon : Tmax by age and dose
	14.2.1.3	Glucagon : AUC0-120 by age and dose
Listing	16.2.5.1	PK profile for each subject
	16.2.5.2	PK Cmax, Tmax, AUC for each subject
Figure	14.4.1.1.subjid	Individual Glucagon profile of each subject
	14.4.1.2	average Glucagon vs time for each age group and dose

6 Mock-ups Tables/Listings/Figures
Table 14.2.1.1 Glucagon: Cmax by age and dose

CATEGORY	Glucagon: Cmax			
	2-6yr 0.5mg	6-12yr 0.5mg	12-18yr 1mg	12-18yr 0.5mg
N	6	6	6	6
Mean (SD)	x.x (x.xx)	x.x (x.xx)	x.x (x.xx)	x.x (x.xx)
Min, Median, Max	x.x (x.xx)	x.x (x.xx)	x.x (x.xx)	x.x (x.xx)

Table 14.2.1.2 Glucagon: Tmax by age and dose

CATEGORY	Glucagon: Tmax			
	2-6yr 0.5mg	6-12yr 0.5mg	12-18yr 1mg	12-18yr 0.5mg
N	6	6	6	6
Mean (SD)	x.x (x.xx)	x.x (x.xx)	x.x (x.xx)	x.x (x.xx)
Min, Median, Max	x.x (x.xx)	x.x (x.xx)	x.x (x.xx)	x.x (x.xx)

Table 14.2.1.3 Glucagon: AUC0-120 by age and dose

CATEGORY	Glucagon: Auc0-120			
	2-6yr 0.5mg	6-12yr 0.5mg	12-18yr 1mg	12-18yr 0.5mg
N	6	6	6	6
Mean (SD)	x.x (x.xx)	x.x (x.xx)	x.x (x.xx)	x.x (x.xx)
Min, Median, Max	x.x (x.xx)	x.x (x.xx)	x.x (x.xx)	x.x (x.xx)

Listing 16.2.5.1 Glucagon of each subject

PATIENT ID	Actual Date/Time	Protocol Time	Glucagon
xxxx	xx/xx/yyyy xx:xx	-5	xx
xxxx	xx/xx/yyyy xx:xx	0	xx
xxxx	xx/xx/yyyy xx:xx	10	xx
xxxx	xx/xx/yyyy xx:xx	20	xx

Listing 16.2.5.2 Glucagon Cmax, TMax, AUC of each subject

PATIENT ID	CMax	TMax	AUC01-20
XXXX	XX	XX	XX
XXXX	XX	XX	XX
XXXX	XX	XX	XX
XXXX	XX	XX	XX

[figure not shown]

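### SAP Appendix II 3.1 fills a missing pre-dose glucagon level by an unspecified straight line through post-dose samples, which can give an implausible time-0 value and shift that subject's AUC0-120

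*SAP*

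**What the plan says.** SAP Appendix II 3.1 gives the sampling grid: "The PK samples are drawn blood at -5, 0, 10, 20, 30, 45, 60, 90, 120, and 180 minutes post dose". If only the time-0 sample is missing, the other pre-dose sample replaces it: "If PK at time 0 minute (T_0) is missing, then PK at -5 minute will be substituted". When neither pre-dose sample is available, the rule reads: "then the PK at later minutes will be used to impute the PK at 0 minute. In such case, linear imputation will be used". The section does not say how many later points are used, whether the line joins two points or is a regression, or what to do with a negative result or one above the 10-minute value.

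Appendix II 3.2.3 takes AUC from time 0 to 120 minutes; it "is calculated using Trapezoidal rule from" the time-0 value onward. No baseline subtraction is stated. Cmax, in 3.2.1, "is defined as the maximum concentration of G-Pen Glucagon after time 0 minute", and Tmax in 3.2.2 is likewise taken after time 0. Appendix II section 4 makes all three variables descriptive, by age group and dose.

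**The concern.** The time-0 concentration should be the level before the study drug was given. Every sample from 10 minutes onward reflects drug already absorbed, so a line drawn back from those samples describes the shape of absorption, not the pre-dose level. The result depends on whether the early rise is flattening or still steepening, and on which points the programmer picks. Two programmers following the same sentence could report different AUC values for the same child.

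What is at stake is that subject's AUC0-120, in groups with a target of six evaluable subjects.

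**Working it through.** The plan states no figure for this rule, so there is nothing to reproduce. The check has three steps.

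**1. Weight of the time-0 value.** On the planned grid the first trapezoid runs from 0 to 10 minutes, so C0 has weight (10 - 0)/2 = 5 minutes, and

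change in AUC = 5 × (imputed C0 - true C0).

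If the 10-minute sample were missing as well, the weight would be (20 - 0)/2 = 10 minutes. That needs three early samples missing and is not in the ranges below.

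**2. Direction.** A line through the 10- and 20-minute samples has slope (C20 - C10)/10, so

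imputed C0 = C10 - 10 × (C20 - C10)/10 = 2·C10 - C20.

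This is too high when C20 - C10 is smaller than C10 - true C0 (the curve is flattening or falling). It is too low when the rise is steeper from 10 to 20 minutes than from 0 to 10. It is negative whenever C20 exceeds 2·C10. The algebra therefore fixes no direction.

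**3. Size, by illustration.** Assumed, because the documents give no concentrations: one-compartment first-order absorption, half-life 30 to 45 minutes, Tmax 10 to 50 minutes, absorption lag 0, 5 or 8 minutes, true pre-dose level zero, Cmax scaled to 1. Examples at half-life 30 minutes, two-point line:

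| Lag (min) | Tmax (min) | C10 | C20 | Imputed C0 | AUC0-120 with true C0 | Change in AUC |
|---|---|---|---|---|---|---|
| 8 | 10 | 1.000 | 0.802 | 1.198 | 45.84 | +13.1% |
| 0 | 10 | 1.000 | 0.862 | 1.138 | 48.76 | +11.7% |
| 0 | 30 | 0.655 | 0.932 | 0.377 | 75.60 | +2.5% |
| 5 | 30 | 0.457 | 0.901 | 0.013 | 69.52 | +0.1% |
| 8 | 30 | 0.237 | 0.870 | -0.396 | 64.84 | -3.1% |
| 0 | 50 | 0.446 | 0.730 | 0.162 | 93.24 | +0.9% |

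First row: 5 × 1.198/45.84 = 13.1%. Fifth row: 5 × (-0.396)/64.84 = -3.1%. Imputed values come from unrounded concentrations.

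Over the whole set:

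- **Line through 10 and 20 minutes:** about -3% to +13%.
- **Least-squares line through all post-dose samples:** about +4% to +9%, always upward. The lowest case (lag 8, Tmax 50, half-life 45) is 5 × 0.737/85.92 = +4.3%.

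A wider set (Tmax about 7 to 73 minutes, lag 0 to 8, true baseline 3% of the peak rise) gives -3.0% to +14.7% for the two-point line, -1.1% to +14.3% for a least-squares line through 10 to 30 minutes, and +3.0% to +8.9% for all post-dose points.

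**Group mean.** If six subjects have similar AUCs and one is affected, the two-point range becomes about -3/6 = -0.5% to 13/6 = +2.2%, and the all-points range about 4/6 = +0.7% to 9/6 = +1.5%.

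**The case against.** The strongest reply is that the case is rare and its effect small. Both pre-dose samples must be missing while early post-dose samples exist. Both are explicit steps in Protocol 10.2.1; at the second, staff are to "collect a second baseline PK blood sample, and begin administration of the study drug". The time-0 value has only a 5-minute weight, Cmax and Tmax are untouched, no PK hypothesis is tested, and individual profiles and AUCs are listed, so an odd value could be traced. All of this stands, and it limits the importance of the point.

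Two stronger readings are tempting, and neither is supported.

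- **AUC is always biased upward.** With a lagged rise, the two-point line gives a value near the truth or below zero. Even an imputed value above the true level need not worsen the AUC. With no lag and Tmax 50 minutes, the sampled trapezoid with the correct zero falls about 0.9% below the continuous-curve AUC, and the imputed version falls within 0.1% of it. Only the all-points line was upward in every profile tried, and the SAP does not say that this line is meant.
- **The youngest children are most exposed because of the blood-volume cap.** Protocol 11.1 says "Early collections (-5 to 30 minutes) will be preferred over later blood draws, and PD samples will be prioritized over PK samples". The first preference protects the pre-dose draws. The second affects post-dose PK samples as much as pre-dose ones. Nothing there drops the -5 and 0 minute PK samples while keeping those at 10 and 20 minutes.

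The reply does not rescue the rule. Rarity and small weight do not make post-dose samples a measure of a pre-dose level, and the sentence cannot be programmed without further choices.

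**Conclusion.** The point holds as a minor one. The rule takes a pre-dose value from samples that carry no measurement of it, and leaves the points and limits of the line open. The imputed value can be implausibly high or negative. The illustrated shift in one subject's AUC0-120 is about -3% to +13% for a two-point line and about +4% to +9% for a line through all post-dose samples. These figures rest on the assumed half-life, Tmax, lag and zero pre-dose level, and are not trial estimates. The documents establish neither the direction of the error, nor how often the rule would be used, nor any age group at greater risk. The primary glucose analysis is not touched.

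**What to change.** In SAP Appendix II 3.1, delete the back-extrapolation. Replace it with one sentence, fixed before the PK data are analysed: if both pre-dose samples are missing, time 0 is set from pre-dose information, for example the median observed pre-dose value of the same age and dose group, and the subject is flagged in the individual PK listing. Reporting that subject's AUC0-120 as missing, while keeping Cmax and Tmax, is equally defensible.

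The cost is one sentence in the SAP, with no protocol change. The downside is that the substituted value comes from other subjects or, under the alternative, that one AUC is lost from a small group.

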1.2.2 Secondary Endpoints

The secondary endpoints for this study are as follows:

- PK parameters, including: descriptive analysis of serum glucagon AUC_{0-180m} , C_{max} and T_{max} of the different age group and overall population. These analyses will be conducted by IMD (See Appendix II).
- PD characteristics, including: descriptive analysis of plasma glucose AUC_{0-90m} , C_{max} , T_{max} and time to achieve an increase in plasma glucose of at least 25 mg/dL for each age group. In addition, in the 12.0-<18.0 year-old age group, plasma glucose change from baseline to 30 minutes after administration of G-Pen™ at a dose of 0.5 mg will be evaluated.
- Safety-related endpoints including:
 - Vital signs, including blood pressure (BP) and heart rate.
 - Incidence of adverse events (AEs) and serious adverse events (SAEs).
 - Subjective injection site discomfort assessed using the Faces Pain Scale (FPS-R).
 - Subjects with sufficient comprehension will further describe the nature and duration of any injection site discomfort using a second questionnaire.
 - Erythema and/or edema formation at site of injection assessed by an investigator using the modified Draize Scale.

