2.4.1 Pharmacokinetic Endpoints

The data for each age group and the overall population will be analyzed descriptively, including serum glucagon AUC_{0-180m} , C_{max} and T_{max} . The analysis will be conducted by IMD (See Appendix II).

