2.4.2 Pharmacodynamic Endpoints

In the 12.0-<18.0 year-old age group, the plasma glucose change from baseline to 30 minutes after administration of G-Pen™ at a dose of 0.5 mg will be evaluated using the same approach described in Section 2.3.1 (Table 8).

Time for plasma glucose to increase by ≥ 25 mg/dL from baseline, maximum glucose concentration (C_{max}) between 0 and 90 min, the time to maximum concentration (T_{max}) will be directly obtained from the observed glucose concentration-time profile. If two identical values are recorded for C_{max} , the first one will be used for T_{max} . The area under the curve from 0 to 90 min (AUC_{0-90m}) of glucose will be calculated as the sum of areas of trapezoids, which are composed of adjacent glucose values. The following rules will be considered:

1. If there are missing data points before the last observed value, they will not be imputed.
2. If there are missing data points after the last observed value, they will be extrapolated using the last two data points.

Baseline-adjusted AUC_{0-90m} with negative values set at 0 will also be calculated. All PD endpoints will be analyzed descriptively for each age group (Table 9) and by treatment dose for subjects aged 12.0-<18.0 (Table 10). Actual time instead of protocol time will be used for calculating the time for plasma glucose to increase by ≥ 25 mg/dL from baseline, T_{max} , AUC_{0-90m} , and baseline-adjusted AUC_{0-90m} . In addition, plasma glucose concentration-time profile by age group (Figure 2 and Table 11) and by treatment dose for subjects aged 12.0-<18.0 (Figure 3 and Table 11) will be presented.

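### The SAP body names glucagon AUC0-180 but Appendix II yields only AUC0-120, and its undefined cubic rule for a missing 120-minute value can extrapolate to impossible concentrations

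*SAP*

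**What the plan says.** **AUC window.** SAP 1.2.2 promises a "descriptive analysis of serum glucagon AUC_{0-180m" (0-180 minutes), SAP 2.4.1 repeats that window, and both assign the work to Appendix II. Appendix II section 2 defines the endpoint as the "area under the curve of G-Pen Glucagon from 0 to 120 minutes". Its section 3.2.3 integrates to 120 minutes, and the only AUC table in its section 5 is "Glucagon : AUC0-120 by age and dose". Protocol 5.3.2 and 13.2.2 also use 0-120 minutes.

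**Missing 120-minute value.** Appendix II 3.1 says: "If PK at 120 minute is missing, then cubic imputation will be used to impute the PK at 120 minute". The one exception is a profile whose last available value is Cmax: "PK never comes down, and then no imputation will be done". Apart from a missing time-0 value, no other missing glucagon value is imputed. For glucose, SAP 2.4.2 does name its points: "If there are missing data points after the last observed value, they will be extrapolated using the last two data points".

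**Late samples may be missing by design.** The protocol's Volume of Blood Draws paragraph (section 11.1) caps collection at 5% of blood volume. It cuts draws for light children, favours samples up to 30 minutes, and ranks glucose samples above glucagon samples.

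**The concern.** There are two defects. First, the AUC named in the SAP body has no definition, calculation or output anywhere.

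Second, the imputation rule is incomplete and too wide. A cubic could mean a polynomial through four points, a natural or not-a-knot spline, a shape-preserving (PCHIP) interpolant or a least-squares fit, and these give different answers. The rule also does not separate interpolation, with a 180-minute value available, from extrapolation beyond the last sample. Cubics extrapolate badly, and the lightest children in the youngest cohort are the most likely to lose late samples.

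With about 6 subjects per cohort summarised by mean, SD, median, minimum and maximum, one bad value can distort the cohort's AUC summary. Two programmers could both follow the text and report different results. Appendix II also does not say whether AUC0-120 is reported for a subject under the Cmax exception, although 3.2.3 runs the integral to 120 minutes.

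**Working it through.** **1. Weights that depend only on the sampling times.** A cubic through the last four points predicts the 120-minute value as a weighted sum of those points, with weight for point i equal to the product over j≠i of (120 - t_j)/(t_i - t_j). On the SAP's times:

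- Last sample 90 (30, 45, 60, 90): -5, 16, -15, 5.
- Last sample 60 (20, 30, 45, 60): -40.5, 100, -96, 37.5.

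Independent errors of equal SD are multiplied by the root sum of squares of the weights: √531 = 23 and √22262.5 = 149. No kinetic assumption enters here.

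**2. One worked profile (assumed).** A one-compartment curve with absorption rate 0.08/min and elimination rate 0.02/min gives 0, 493, 625, 611, 506, 391, 219, 121, 36 at 0, 10, 20, 30, 45, 60, 90, 120, 180 minutes.

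- Ending at 60: -40.5×625 + 100×611 - 96×506 + 37.5×391 = 1874 (1889 before rounding), against a true 121 and a peak of 625.
- Trapezoidal AUC0-60 is 29340. The true AUC from 60 to 120 is 9150 + 5100 = 14250, total 43590. With the imputed value, the last piece is (391 + 1889)/2 × 60 = 68400, total 97740, an error of +124%.
- Ending at 90, the imputed value is 274.

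**3. Range over profiles and methods.** Four assumed noise-free profiles were used, with absorption/elimination time constants (8, 20), (15, 25), (25, 35) and (30, 45) minutes and baseline 0. Sampled Tmax is 10-30 minutes and the true 120-minute level is 1-35% of Cmax. Each was imputed by four interpolating cubics: last four points, not-a-knot spline, natural spline and PCHIP. Implausible means negative or above the observed peak.

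| Samples available | Implausible | AUC0-120 error |
|---|---|---|
| 180 observed, 120 missing | 1 of 16 (-0.002 × Cmax) | -1% to +3% |
| Last at 90 | 4 of 16 | -11% to +11% |
| Last at 60 | 14 of 16 | -207% to +220% |
| Last at 45 | 16 of 16 | not tabulated |
| Last at 30 | 8 of 8 (2 profiles exempt) | not tabulated |

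By method, with the last sample at 60:

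| Cubic | Imputed value / Cmax | AUC0-120 error |
|---|---|---|
| Last four points | 1.4 to 3.7 | +60% to +215% |
| Not-a-knot | 1.2 to 3.0 | +52% to +173% |
| Natural spline | -2.5 to 1.4 | -207% to +39% |
| PCHIP | -0.03 to 3.3 | 0% to +220% |

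The two plausible results (natural spline 0.56 and PCHIP 0.14 × Cmax) come from one profile. A least-squares cubic on all points, which the SAP does not exclude, is negative in 4 of 4 profiles even with the 180-minute value observed (AUC -25% to -7%).

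**4. Effect on a cohort of 6.** One affected subject moves the expected mean by one sixth of that subject's error.

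- Last sample 60, last-four-point method: 60/6 = +10% to 215/6 = +36%. The median moves +6% to +13% and the SD is multiplied by 1.1 to 3.5 (between-subject CV assumed 30-50%).
- Last sample 60, all four methods: -207/6 = -35% to 220/6 = +37%.
- Last sample 90: 11/6, about ±2%.

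**5. Which children lose the 120-minute sample.** Protocol Table 4 gives 20 bedside glucose samples × 2 mL = 40 mL, plus 10 glucagon samples × 2 mL = 20 mL, so 60 mL when a CGM is used in induction. If the latest glucagon draws are dropped first (assumed), the 120-minute draw is lost when less than 58 mL is allowed. At an assumed 70-80 mL blood per kg:

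- With CGM: 58/(0.05×80) = 14.5 kg to 58/(0.05×70) = 16.6 kg.
- Without CGM (80 mL visit): 78/(0.05×80) = 19.5 kg to 78/(0.05×70) = 22.3 kg.
- Each further 2 mL draw spans 0.5-0.6 kg.

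**6. The two windows.** AUC0-180 exceeds AUC0-120 by 0.7% to 16% on the four profiles, and by 4% to 19% on a second assumed set (absorption rates 0.05-0.12/min, elimination rates 0.015-0.03/min). They are not interchangeable.

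**The case against.** The window conflict is close to a labelling slip. The protocol and Appendix II agree on 0-120 minutes, so the protocol's endpoint is still produced. That is fair, but the SAP body then names an endpoint that nobody will deliver.

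The large errors need sampling to stop at 60 minutes or earlier. The protocol sets no order among the glucagon draws after 30 minutes, so a site could drop the 45- or 60-minute sample and keep 90 or 120. Even with latest-first dropping, ends at 60, 45 and 30 minutes together span only 1.5-1.7 kg of body weight. The first step of loss, ending at 90, moves a cohort mean by about 2%. All of this stands and limits how often serious harm is likely. It does not make the rule sound where it applies.

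The counts depend on which cubics are tried, and the +10% to +36% cohort shift belongs to one method. Also true: across the four methods the shift can go either way, which itself shows that the rule is undefined.

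The natural reading of the Cmax exception is that no AUC0-120 is reported. That is reasonable, and one sentence would settle it.

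Finally, the endpoint is descriptive, and an absurd value would be visible in the minimum, maximum and listings. It would, but no rule says what to do with it once seen.

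**Conclusion.** The concern holds. The window conflict and the missing definition follow from the text alone. The instability of a four-point cubic follows from the sampling times alone.

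The size of the error rests on assumed, noise-free kinetics. It is negligible for interpolating cubics with the 180-minute value present, modest when sampling ends at 90 minutes, and large with uncertain sign at 60 minutes or earlier. Noise-free curves understate the problem for the four-point reading. The weight thresholds rest on an assumed 70-80 mL/kg and latest-first dropping. The documents give no body weights, so the frequency cannot be estimated.

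The damage is confined to a secondary descriptive glucagon summary, most likely in the youngest cohort. The primary glucose test is not touched.

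**What to change.** - Use one glucagon AUC window throughout. AUC0-120 matches the protocol and Appendix II. If 0-180 is intended, add its definition and output to Appendix II.
- Impute the 120-minute value only when the 180-minute value is observed, by a named interpolation between the 90- and 180-minute samples. On the four assumed profiles the AUC0-120 error is +0.6% to +1.7% for linear and -0.3% to 0% for log-linear.
- Otherwise do not extrapolate by a cubic. List AUC to the last observed time, leave the subject out of the AUC0-120 summary, and show the number left out.
- Treat subjects under the Cmax exception the same way, and say so.
- Log-linear terminal extrapolation can be an optional sensitivity analysis.

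The cost is SAP and Appendix II wording only. The downside is fewer AUC0-120 values, mainly from the lightest children, so the youngest cohort's summary leans toward heavier children. The count and the listing make that visible. Log-linear extrapolation as the main rule would keep those subjects, at the price of relying on an assumed terminal decline.
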